### **3.4 Exclusion Criteria**

- HIV-2 infection

### **3.5 Subgroups of study population**

The study population will be divided to several subgroups based on the baseline demographic and clinical characteristic which are the following:

- 1) Age: < 40, 40-60, > 60 years;
- 2) Gender: male, female, transgender;

- 3) Employment status: employed, unemployed, student, pensioner, incarcerated;
- 4) Marital status: married, single, divorced;
- 5) Substance abuse: no, alcohol, drugs;
- 6) HIV diagnosis duration at baseline: 0-0.5, 0.5-1, 1-2, 2-3, 3-5, >5 years;
- 7) Route of infection: IV drug use, homosexual (MSM), heterosexual, other;
- 8) HIV stage (if applicable): I-V;
- 9) Baseline viral load: <50 000, 50 000-100 000, >100 000 copies/ml;
- 10) Baseline CD4 cells count: <50, 50-100, 101-200, 201-350 and >350 cells/µl;
- 11) Concomitant medications at baseline: 0, 1-2, 3-5, >5;
- 12) Comorbidities at baseline: No, Yes CV disease, diabetes mellitus, CK disease, liver disease, viral hepatitis, pulmonary disease, tuberculosis, CNS disease, psychiatric disorder;
- 13) ART therapy: NNRTI plus two NRTIs; PI boosted by ritonavir with 2 NRTIs.

## 4 Variables and Outcomes

### 4.1 Patient Demographics

The following demographic parameters will be retrospectively recorded at baseline:

- Age (years);
- Gender: male, female, transgender;
- Employment status: employed, unemployed, student, pensioner, incarcerated;
- Marital status: married, single;
- Substance abuse: no, alcohol, drugs.

### 4.2 Clinical Variables

The following clinical parameters will be retrospectively recorded at baseline:

- 1) HIV diagnosis duration at baseline (years);
- 2) Route of infection: IV drug use, homosexual (MSM), heterosexual, other;
- 3) HIV stage (if applicable): I-V;
- 4) Baseline viral load (copies/ml);
- 5) Baseline CD4 cells count (cells/µl);
- 6) Concomitant medications at baseline;
  - a. Data will be retrospectively captured on medication given for the treatment for any disorder/disease but HIV/AIDS at baseline

- 7) Comorbidities at baseline: No, Yes – CV disease, diabetes mellitus, CK disease, liver disease, viral hepatitis, pulmonary disease, tuberculosis, CNS disease, psychiatric disorder;
- 8) ART therapy: NNRTI plus two NRTIs; PI boosted by ritonavir with 2 NRTIs.

It should be noted that demographic and clinical variables collected in this non-interventional retrospective study are recommended for daily-practice clinical record keeping for the management of HIV-infection in Russia. Thus, these variables are available for the majority of the HIV-infected patients in regular clinical practice and can be collected within locally applicable legal and ethical framework for non-interventional research.

### 4.3 Outcomes

#### 4.3.1. Treatment Durability

Treatment durability is determined as a percentage of patients continuing their first-line ART with NNRTI plus 2 NRTIs or PI boosted by ritonavir with 2 NRTIs for 48 and 96 weeks without change of the NNRTI or PI agent (“anchor” or “third agent”) within the class or without change of the NNRTI or PI agent to a different class.

According to the Primary objective, the treatment durability is to be retrospectively evaluated at 48 weeks from the time of initiation.

According to the Exploratory objective, the treatment durability is to be retrospectively evaluated at 96 weeks from the time of initiation.

#### 4.3.1. Time on therapy

According to the Secondary objective, the estimated time on therapy (weeks) without change of the NNRTI or PI agent (“anchor” or “third agent”) is to be retrospectively evaluated at week 48 from the time initiation.

According to the Exploratory objective, the estimated time on therapy (weeks) without change of the NNRTI or PI agent (“anchor” or “third agent”) is to be retrospectively evaluated at week 48 from the time initiation.

#### 4.3.2. Association between of patients characteristics and treatment durability

[figure not shown]
According to the Secondary objective, association between clinical and demographic characteristics of patients and treatment durability at 48 weeks will be retrospectively evaluated.

According to the Exploratory objective, association between clinical and demographic characteristics of patients and treatment durability at 96 weeks will be retrospectively evaluated.

## 5 STUDY PROCEDURES OF DATA COLLECTION

The Study Flow Chart and Study Procedures Table summarize the procedures of data collection to be performed retrospectively. Individual study procedures of retrospective data collection are described in detail below.

## Study Flow Chart

## Study Procedures

Study period	Screening	Retrospective clinical data extraction through chart or medical records review
Visit Number	0	1
Screening and chart review	X	
Informed consent	X	
Inclusion/Exclusion criteria	X	
Age at baseline		X
Gender at baseline		X
Employment status at baseline		X
Marital status at baseline		X
Substance abuse		X
HIV diagnosis duration at baseline		X
Route of infection at baseline		X
HIV stage at baseline		X
Viral load at baseline		X
CD4 at baseline		X
Concomitant medications at baseline		X
Comorbidities at baseline		X
Initial ART at baseline		X
Treatment durability: NNRTI or PI continuation at Week 48/96		X
Estimated time on treatment with NNRTI or PI at Week 48/96		X
Adverse events at baseline and at Week 48/96		X

## **5.1 General Informed Consent**

Consent must be documented by the subject's dated signature or by the subject's legally acceptable representative's dated signature on a consent form along with the dated signature of the person conducting the consent discussion.

A copy of the signed and dated consent form should be given to the subject before the demographic and clinical data are extracted through retrospective chart or medical records review.

The initial informed consent form, any subsequent revised written informed consent form and any written information provided to the subject must receive the IRB/ERC's approval/favorable opinion in advance of use. The informed consent will adhere to IRB/ERC requirements, applicable laws and regulations and Sponsor requirements.

## **5.2 Withdrawal/Discontinuation**

The patient may withdraw his/her consent to participate in the study at any time for any reason. This decision will not have any consequences for his/her future medical care. The sponsor may stop the study at any time. In such case, all investigators will be informed in advance.

## **5.3 Retrospective Data Collection (Clinical Assessments)**

This retrospective study will only involve Secondary Data Collection by reviewing medical chart generated in routine clinical cares.

Data will be retrospectively collected from up to 8 investigational sites with up to 200 patients recruited per site. It is planned that the first half of the study population (500 patients) will be enrolled during the first 6-9 months and the second half of the study population (500 patients) during the second 6-9 months of the study.

Based on the protocol, an electronic data capture (EDC) or electronic clinical reporting form (eCRF) will be developed for data collection. Each local center will be asked to enter the data into the EDC. All the data collected will be entered into a single database stored centrally and analyzed.

If any reportable safety events are identified during retrospective chart review, it is to be ensured they are reported as per section 6 of the protocol.

## **5.4 Interim Statistical Analysis**

Interim Statistical Analysis will be performed when data retrospectively collected from at least 500 patients during the first 6-9 months of the study.

## 6 Safety Reporting and Related Procedures

### Adverse Event Reporting Language for Non-Interventional Study Protocols

#### Introduction

This is a non-interventional study based on secondary use of data collected for other purposes. No administration of any therapeutic or prophylactic agent is required in this protocol, and there are no procedures required as part of this protocol.

#### 6.1 Adverse Event and Product Quality Complaint Reporting

##### 6.1.1 INVESTIGATOR RESPONSIBILITY:

Although adverse events (AEs) and product quality complaints (PQCs) are not actively solicited in this study, there are certain circumstances in which individual AEs and/or PQCs will be reported. For example, during review of medical records or physician notes (paper or electronic), to collect data as required by the protocol, if a notation of an AE\* or PQC to any Merck product is identified, the AE/PQC must be reported according to Table 1.

\*For the purposes of this protocol, the term “AE” collectively refers to the following reportable events (refer to section 6.2 for definitions):

- Serious adverse reactions (SARs), including death
- Non-serious adverse reactions (NSARs)
- Special situations
- Study-specific Health Outcomes of Interest (HOIs) that meet criteria for SAR/NSAR or special situation

AEs, PQCs, and AEs that occur in combination with PQCs, or spontaneously reported events, should all be captured using the AE/PQC report form for each patient and reported according to Table 1.

**Table 1: AE and PQC Reporting Timeframes and Process for Investigators**

AEs AND PQCs	INVESTIGATOR TIMEFRAMES Investigator to MSD [1]
SAR (including study-specific HOIs that meet criteria for SAR Serious Special Situation, regardless of causality)	24 hours from receipt
NSAR (including study-specific HOIs that meet criteria for NSAR) Non-serious Special Situation, regardless of causality	10 CD from receipt
PQC with or without an AE (SAR/NSAR/Special situation)	24 hours from receipt
Spontaneously reported AEs/PQCs for Merck products-submit using above timeframes	
Follow-up to any AE/PQC-submit using above timeframes	
BD-Business Day; CD-Calendar Day	

If the investigator elects to submit AEs/PQCs for **non-MSD products**, they should be reported to the market authorization holder (MAH) for that product or to the health authority according to the institution's policy or local laws and regulations.

**[1] Investigator to MSD:** AEs and PQCs for MSD products are submitted to MSD for reporting to worldwide regulatory agencies as appropriate.

**Submitting AEs and PQCs to Local Designated Point of Contact (DPOC):** All AEs and PQCs must be submitted to Local DPOC Mailbox [contact] in English using the AE/PQC reporting form.

## 6.2 DEFINITIONS

### 6.2.1 Adverse Event (AE)

Any untoward medical occurrence in a patient or clinical investigation subject administered sponsor's product and which does not necessarily have to have a causal relationship with this product. An adverse event can therefore be any unfavorable and unintended sign (including an abnormal laboratory finding, for example), symptom, or disease temporally associated with the use of the product, whether or not considered related to the product. Any worsening (i.e., any clinically significant adverse change in frequency and/or intensity) of a preexisting condition that is temporally associated with the use of the product, is also an adverse event.

### 6.2.2 Adverse Reaction (AR); also referred to as Adverse Drug Reaction (ADR)

An AE which has a causal relationship with the product, that is, a causal relationship between the product and the adverse event is at least a reasonable possibility.

### 6.2.3 Serious Adverse Event (SAE)/Serious Adverse Reaction (SAR)

An adverse event or adverse reaction that results in death, is life threatening, results in persistent or significant disability/incapacity, requires inpatient hospitalization, prolongation of existing inpatient hospitalization, is a congenital anomaly/birth defect, or is another important medical event. Other important medical events that may not result in death, may not be life-threatening, or may not require hospitalization may be considered an SAE/SAR when, based upon appropriate medical judgment, they may jeopardize the patient or subject and may require medical or surgical intervention to prevent one of the other outcomes listed previously. Examples of such medical events include allergic bronchospasm requiring intensive treatment in an emergency room or at home and blood dyscrasias or convulsions that do not result in inpatient hospitalization.

### 6.2.4 Non-serious Adverse Reaction (NSAR)

An adverse reaction that does not meet any of the serious criteria in 6.2.3.

### 6.2.5 Special Situations

The following special situations are considered important safety information and must be reported, regardless of seriousness or causality, if the investigator becomes aware of them:

- Overdose
- Exposure to product during pregnancy or lactation
- Lack of therapeutic effect
- Off-label use, medication error, misuse, abuse, or occupational exposure
- Suspected transmission via a medicinal product of an infectious agent

- Unexpected Therapeutic Benefit/Effect

### **6.2.6 Health Outcome of Interest (HOI)**

Health Outcomes of Interest (HOIs) are clinical events or outcomes that are collected according to the protocol. HOIs may be represented as diagnoses, treatments or procedures. Examples of HOIs include syncope, disease progression, or hypoglycaemia collected as study endpoints. HOIs may meet the criteria of an SAE/SAR, NSAR or special situation, and if so, must be collected as such, in addition to being collected as an HOI. Specifically, collected HOI data must be assessed for the criteria described herein and reported accordingly.

### **6.2.7 Product Quality Complaint (PQC)**

Any communication that describes a potential defect related to the identity, strength, quality, purity or performance of a product identified by an external customer. This includes potential device or device component malfunctions.

### **6.2.8 Malfunction**

The failure of a device (including the device component of a combination product) to meet its performance specifications or otherwise perform as intended. Performance specifications include all claims made in the labeling for the device.

### **6.2.9 Sponsor's Product**

Sponsor's product includes any pharmaceutical product, biological product, device, diagnostic agent or protocol-specified procedure, whether investigational (including placebo or active comparator product) or marketed, manufactured by, licensed by, provided by or distributed by the Sponsor for human use.

### **6.2.10 Causality Assessment**

A causality assessment is the determination of whether or not there is at least a reasonable possibility that a product caused the adverse event. Causality must be recorded on the AE form for each reported event in relationship to a Sponsor's product.

#### **Secondary Data Collection**

Only AEs with an explicit and definitive notation (by a healthcare provider) of a causal relationship with a product in the medical records or other secondary data being reviewed should be reported as NSAR/SARs. During review of secondary data, causality should never be assigned retrospectively.

## **7 Statistical Analysis Plan**

### **7.1 Statistical Methods**

Data will be presented descriptively as follows: the number of observations, mean and standard deviation, median, first and third quartiles, minimum and maximum for continuous variables, and the absolute frequencies and percentage of patients presenting the given feature for qualitative variables. The results on the study endpoints (proportion of patients who remain on first-line ART at 48 and 96 weeks) will be presented with two-

sided 95% confidence intervals. Univariate and multivariate logistic regression will be used to study the association between patients' baseline demographic and clinical characteristics and treatment discontinuation status.

#### **7.1.1 Primary Objective:**

- Percentage of HIV-infected patients remained on first-line ART at 48 weeks after the start of treatment will be presented descriptively with 95% confidence interval by initial ART regimen (NNRTI or boosted PI plus 2 NRTIs) and overall

#### **7.1.2 Secondary Objectives:**

- Time on therapy (weeks) without change of the NNRTI or PI agent at week 48 from the ART initiation will be presented in Kaplan-Meier plots
- Demographic and clinical characteristics at baseline will be presented descriptively by initial ART regimen (NNRTI or boosted PI plus 2 NRTIs) and overall
- Association between characteristics of patients and treatment durability at 48 weeks will be investigated via:
  - Subgroup analysis: number and percent of patients continuing treatment at 48 weeks will be presented descriptively by demographic and clinical characteristics categorized according to 8.1.4
  - Multivariate logistic regression analysis to identify potential risk factors for discontinuation of initial ART at 48 weeks. Demographic and clinical characteristics categorized according to 8.1.4 will be included into multivariate analysis only if they are found significant in univariate logistic regression analysis. Unadjusted (univariate model) and adjusted (multivariate model) odds ratios will be presented with 95% confidence intervals for the parameters included in each of the analyses.
- Percentage of HIV-infected patients remained on first-line ART at 96 weeks after the start of treatment will be presented descriptively with 95% confidence interval by initial ART regimen (NNRTI or boosted PI plus 2 NRTIs) and overall
- Time on therapy (weeks) without change of the NNRTI or PI agent at week 96 from the ART initiation will be presented in Kaplan-Meier plots
- Association between characteristics of patients and treatment durability at 96 weeks will be investigated via:
  - Subgroup analysis: number and percent of patients continuing treatment at 96 weeks will be presented by demographic and clinical characteristics categorized according to 8.1.4

- Multivariate logistic regression analysis to identify potential risk factors for discontinuation of initial ART at 96 weeks. Demographic and clinical characteristics categorized according to 8.1.3 will be included into multivariate analysis only if they are found significant in univariate logistic regression analysis ( $p<0.1$ ). Unadjusted (univariate model) and adjusted (multivariate model) odds ratios will be presented with 95% confidence intervals for the parameters included in each of the analyses.

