### **3.3 Inclusion Criteria**

- Adult patients (>18 years of age) with definite HIV-1 infection based on positive lab test and judgement of treating physician according to standards of care
- Naive to antiretroviral treatment at the time of initiation
- Viral load of >1000 copies/ml at the time of initiation of ART
- Initiated their first-line ART between February 01 and June 30, 2017
- Patients are included, if the third component of their first line ART was either NNRTI or boosted PI plus 2 NRTIs
- Completed follow-up from baseline for at least 96 weeks
- Signed informed consent

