### 7.1.3 Subgroup analysis

The study population will be divided to several subgroups based on the baseline demographic and clinical characteristics. The following categories will be used for the subgroup analysis:

- 1) Age: < 40, 40-60, > 60 years;
- 2) Gender: male, female, transgender;
- 3) Employment status: employed, unemployed, student, pensioner, incarcerated;
- 4) Marital status: married, single, divorced;
- 5) Substance abuse: no, alcohol, drugs;
- 6) HIV diagnosis duration at baseline: 0-0.5, 0.5-1, 1-2, 2-3, 3-5, >5 years;
- 7) Route of infection: IV drug use, homosexual (MSM), heterosexual, other;
- 8) HIV stage (if applicable): I-V;
- 9) Baseline viral load: <50 000, 50 000-100 000, >100 000 copies/ml;
- 10) Baseline CD4 cells count: <50, 50-100, 101-200, 201-350 and >350 cells/ $\mu$ l;
- 11) Concomitant medications at baseline: 0, 1-2, 3-5, >5;
- 12) Comorbidities at baseline: No, Yes CV disease, diabetes mellitus, CK disease, liver disease, viral hepatitis, pulmonary disease, tuberculosis, CNS disease, psychiatric disorder;
- 13) ART therapy: NNRTI plus two NRTIs; PI boosted by ritonavir with 2 NRTIs.

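### Age, diagnosis duration, viral load and CD4 are recorded as numbers, but the risk-factor regressions use only bands, which costs power for weak to moderate graded associations

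*Combined protocol and SAP*

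**What the plan says.** Section 4.1 records age in years. Section 4.2 records diagnosis duration in years, viral load in copies/ml and CD4 count in cells/µl.

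Section 7.1.2 plans univariate and then multivariable logistic regression to find risk factors for discontinuing initial ART. For week 48: "Demographic and clinical characteristics categorized according to 8.1.4 will be included into multivariate analysis only if they are found significant" in the univariate model, with no significance level stated. For week 96: "Demographic and clinical characteristics categorized according to 8.1.3 will be included into multivariate analysis", subject to univariate p<0.1. No continuous, spline or trend-coded term is planned.

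Neither cross-reference works. Section 8.1.4 does not exist, and 8.1.3 deals with confidentiality of investigator information. The analysis bands appear in 7.1.3, which repeats the list in 3.5. They include "Baseline viral load: <50 000, 50 000-100 000, >100 000 copies/ml" and "Baseline CD4 cells count: <50, 50-100, 101-200, 201-350 and >350", three bands for age and six for diagnosis duration. That these bands feed the regressions is an inference, but no other reading fits the text.

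**The concern.** These regressions serve stated secondary objectives at 48 and 96 weeks, and 1.2 gives prognostic factors as part of the rationale. Banding a measured variable treats patients within a band as identical and spends several parameters on what may be a simple gradient. Because a characteristic enters the multivariable model only if it passes the univariate screen, a real gradient that the bands fail to detect is dropped from the adjusted model altogether.

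The viral-load bands are also uneven on the log scale on which that marker is usually handled. Entry requires "Viral load of >1000 copies/ml at the time of initiation of ART", so the lowest band is far wider than the middle one. A patient at 1 500 copies/ml is grouped with one at 49 000, while 49 000 and 51 000 are separated.

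**Working it through.** **The plan's own figure.** Section 7.3 sizes the study on precision only. For N=1000: 0.70 ± 1.96 × √(0.70 × 0.30/1000) = 0.70 ± 0.0284, or 67.16% to 72.84%, width 5.68%. This matches the stated 67.2% to 72.8%, width 5.7%. No power is given for the regressions.

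**Band widths.** Lowest viral-load band: log10(50 000/1 000) = 1.70. Middle band: log10(100 000/50 000) = 0.30.

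**Degrees of freedom.** Age 2, viral load 2, CD4 4, duration 5: 13 in all. Four 3-knot splines use 4 × 2 = 8.

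**Inputs for power.** From the documents: N=1000, 30% discontinuing at 48 weeks, viral load above 1 000. Assumed, because the documents give no distributions or effect sizes:

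- Set A: log10 viral load normal (mean 4.7, SD 0.8), truncated at 3; square-root CD4 normal (mean 17, SD 6), effect linear on the root scale. The viral-load bands then hold 49%, 15% and 36% of patients.
- Set B: log10 viral load normal (4.7, 0.7), truncated at 3; square-root CD4 normal with median count 300 and SD 5.5, effect linear in the count. The two lowest CD4 bands then hold 3.1% and 6.0%, or about 31 and 60 of 1000 patients.

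**Effect size.** 80% power for a 1-df test at 5% needs a noncentrality of (1.960 + 0.842)² = 7.85. With noncentrality about N × 0.3 × 0.7 × β² = 210β², β = √(7.85/210) = 0.193, an OR of about 1.21 per SD. At the same noncentrality a 2-df spline test has 71% power, which is the price of not assuming linearity.

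**Simulated power, univariate likelihood-ratio test:**

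| Truth, test level | Variable | Linear | Spline | Bands |
|---|---|---|---|---|
| OR 1.22/SD, 5% (A) | Viral load | 83% | 75% | 61% |
| OR 1.22/SD, 5% (A) | CD4 | 83% | 74% | 54% |
| OR 1.21/SD, 5% (B) | Viral load | 81% | 70% | 56% |
| OR 1.21/SD, 5% (B) | CD4 | 80% | 71% | 46% |
| OR 1.30/SD, 5% (B) | Viral load | 97% | 94% | 85% |
| OR 1.30/SD, 5% (B) | CD4 | 97% | 94% | 75% |
| OR 1.35/SD, 5% (A) | Viral load | – | 98% | 90% |
| OR 1.35/SD, 5% (A) | CD4 | – | 98% | 92% |
| Step OR 1.5 above 100 000, 5% (B) | Viral load | 60% | 54% | 73% |
| Step OR 1.5 up to 200, 5% (B) | CD4 | 46% | 54% | 57% |

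Repeat runs at OR about 1.2 fall within 80-84% (linear), 70-76% (spline) and 46-61% (bands). Under set A at a 10% screen and OR 1.22, bands give about 66-74% and a spline about 83%.

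**All four variables, wider assumptions.** A noncentral chi-square calculation fixed the linear term at 80% power (5% level) and varied the distributions: median CD4 200-400, median age 33-42, median duration 0.5-3 years, mean log10 viral load 4.3-5.0. Power with the bands was 52-57% for viral load, 37-51% for CD4, 51-60% for age and 35-51% for duration. Regaining 80% with bands would take about 1570 to 2670 patients. That is equivalent to discarding 1 − 1000/1570 = 36% to 1 − 1000/2670 = 63% of the sample relative to a correctly specified linear term. At OR 1.50 per SD the bands reach 96-100%.

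**The case against.** The strongest case for the plan has four parts.

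1. **The bands are prespecified.** They stand in 3.5 and 7.1.3, so cut-points cannot be chosen from the data. This stands, and it counts in the plan's favour.
2. **The plan disclaims hypothesis testing** (7.1.4 and 7.3), so power might seem beside the point. This does not stand: 7.1.2 uses significance to decide which variables enter the model.
3. **The loss depends on the truth.** It is small for strong effects, and a step at a band edge reverses the ranking. This stands. The documents state no threshold hypothesis, but they do not exclude one.
4. **A linear term is too generous a comparator**, because it assumes the shape that generated the data. This also stands. The fair comparison is spline against bands, a gain of about 14 to 25 points in the table at OR about 1.2.

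A reader might infer two stronger things. One is that banding leaves the NNRTI-versus-PI odds ratio under-adjusted for disease stage. The documents do not support making that a finding: no objective compares the regimens, regimen is one of 13 listed factors, HIV stage is itself a candidate covariate, and no size of residual confounding can be derived. The other is that all four variables are coarsely cut. Three bands for age and viral load are coarse. With five for CD4 and six for duration, much of the loss comes from extra parameters and, if CD4 counts are high, thinly filled low bands.

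**Conclusion.** The point holds as a limited improvement to the secondary association analyses. Numeric data are collected and then entered into the regressions only as bands, through section references that need correcting in any case. For a weak to moderate graded association of viral load or CD4, about OR 1.2 per SD, the bands leave roughly a coin-toss chance of detection at 5%, against about 70-76% with a spline. At the 10% screen the gap is narrower.

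The size rests on assumed covariate distributions and a roughly graded effect. Under set A the gap is only 6 to 8 points at OR 1.35 per SD. It is not a general loss of power, and bands win where risk steps at a band edge. The primary 48-week percentage and its precision are unaffected.

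**What to change.** In 7.1.2:

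- Replace the references to 8.1.4 and 8.1.3 with 7.1.3.
- Keep the 7.1.3 bands for the descriptive subgroup tables.
- In the univariate and multivariable models at both time points, enter log10 viral load, square-root CD4, age and diagnosis duration as continuous terms, each with a 3-knot restricted cubic spline. Test both spline terms of a variable jointly at the univariate screen.
- Report odds ratios as contrasts between named values, for example the 25th versus the 75th percentile. A splined term has no single odds ratio per unit, so per-unit values belong only with a linear term.
- Keep the banded model as a sensitivity analysis for threshold effects.

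The cost is SAP wording; no new data are needed. The downsides are a less direct per-band reading and some lost power if the true effect is a step at a band edge, which the sensitivity analysis partly covers.
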